5.5 Concomitant Medications and Treatments

All medications or treatments ongoing at the screening visit or taken within the previous 30 days must be recorded on the prior and concomitant medications CRF.

Any medication the patient takes during his or her study participation is considered a concomitant medication. This applies to prescription and over-the-counter (OTC) drugs and to herbal supplements, whether taken systemically or applied topically. In addition, any treatment the patient receives other than the study medication is considered a concomitant treatment. All concomitant medications and concomitant treatments must be recorded in the CRFs. Prohibited medication classes and treatments are described in the Exclusion Criteria. In the event that a prohibited treatment is received, it must be documented on the CRFs.

Subjects will not be allowed to use any of the prohibited medications listed in the exclusion criteria during the course of this study and up to 30 days prior to the start of the study. Subjects will be allowed the use of birth control, vitamins, or supplements.

6 VARIABLES AND METHODS

6.1 Safety

6.1.1 Adverse Events

Illnesses present at study entry are considered pre-existing conditions and will be documented as medical history on the CRF provided. All adverse events, including intercurrent illnesses and worsening of pre-existing conditions, must be reported and documented as described below.

6.1.1.1 Definitions

An adverse event is any untoward medical event that occurs in a patient or subject administered a pharmaceutical product and that does not necessarily have a causal relationship with this treatment. An AE can therefore be any unfavorable and unintended sign (including abnormal laboratory findings), symptom, or disease temporally associated with the investigational product, whether or not related to the investigational product.

6.1.1.2 Assessment of Adverse Events

Volunteered, observed, and elicited reports of adverse events will be recorded. This includes adverse events the patient reports spontaneously, those the investigator observes, and those the investigator elicits in response to open-ended questions at the times indicated on the Schedule of Observations. At each visit, the patient should be asked a non-leading question such as: "Do you feel different in any way since your last treatment visit?" Subjects will also be questioned concerning possible skin reactions according to a specific checklist of possible adverse events.

Each adverse event will be assessed by the investigator with regard to the following categories.

Serious/Not Serious

International Conference on Harmonization (ICH) Guidelines and US Federal Regulations define a serious adverse event (SAE) as any untoward medical occurrence that at any dose:

- Results in death.
- Is life-threatening. This means that the patient is at risk of death at the time of the event; it does not mean that the event hypothetically might have caused death if it were more severe.
- Requires or prolongs hospitalization (hospitalization defined as ≥ 24 hours).
- Results in persistent or significant disability or incapacity.
- Is a congenital anomaly or birth defect.
- Important medical events that may not be immediately life-threatening or result in death or hospitalization, but that may jeopardize the patient or require intervention to prevent one of the above outcomes, usually should also be considered serious. Events are considered serious if they result in life threatening events, death, genetic abnormality, persistent disability, or prolonged hospitalization. Examples include pregnancy, allergic bronchospasm requiring treatment at home or in the emergency room, and blood dyscrasias or convulsions not resulting in hospitalization. Medical and scientific judgment should be used to determine whether such events should be considered serious.

- Pregnancy should always be considered as a serious adverse event. As such, pregnancy should be recorded on the adverse event page of the CRF and a serious adverse event form completed and submitted as described.

Serious adverse events will be reported to the IRB/sponsor no more than 7 business days from the beginning of the event.

Severity

The severity of each adverse event must be assessed and recorded on the Adverse Event CRF as mild, moderate, or severe.

Mild:	An adverse event that is usually transient, requires no special treatment, and does not interfere with usual activities.
Moderate:	An adverse event that interferes with usual activities but may be ameliorated by therapeutic measures.
Severe:	An adverse event that is intense or debilitating and that interferes with usual activities. Recovery is usually aided by therapeutic measures and may require the discontinuation of study medication.

Relationship to Study Treatment

The investigator will assess the relationship between the study medication and the adverse event as probable, possible, unlikely, or unrelated as follows.

Probable:	Reports including good reasons and sufficient information to assume a causal relationship in the sense that it is plausible, conceivable, or likely.
Possible:	Reports containing sufficient information to indicate the possibility of a causal relationship in the sense of it not being impossible and not unlikely, although the connection may be uncertain or doubtful (e.g., due to missing data, insufficient evidence, etc.).
Unlikely:	Reports of a clinical event, including laboratory test abnormality, with a temporal relationship to drug administration which makes a causal relationship improbable, and in which other drugs, chemicals, or underlying disease provide plausible explanations.
Not Related:	Reports excluding the possibility of a relationship between the event and the drug treatment, i.e., no reasonable suspected causal relationship to study medication administration.

6.1.1.3 Recording Adverse Events

All adverse events, regardless of relationship to study treatment, must be recorded on the Adverse Event CRF. All adverse events reports should contain the date the adverse events occurred, a brief description of the event, time of onset, end date or duration of event (if less than 24 hours), intensity, treatment required, relationship to study treatment, action taken, outcome, and whether the event is classified as serious.

6.1.1.4 Follow-Up of Adverse Events

Reporting of adverse events will terminate on the last day of study follow-up. The investigator must follow non-serious events possibly related to the study treatment and all serious adverse events until they resolve or until the investigator assesses them as chronic or stable.

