4 STUDY POPULATION

4.1 Inclusion Criteria

Subjects who meet all of the following criteria are eligible for this study:

1. Subject is a male or non-pregnant female, 12 years of age and older.
2. Subject is willing and able to provide written informed consent for the study.
3. Subject is willing and able to apply the investigational product as directed, comply with study instructions and commit to all follow-up visits for the duration of the study.
4. Subject has clinical diagnosis of mild to moderate hand dermatitis for at least 3 months.
5. Subject has a baseline Investigator's Global Assessment (IGA) score of 2 or 3 (disease severity of mild or moderate).
6. Subject is in good general health and free of any disease state or physical condition that might impair evaluation of hand dermatitis or which, in the investigator's opinion, exposes the subject to an unacceptable risk by study participation.
7. Women of childbearing potential (WOCBP) must use an effective method of birth control or must be post-menopausal or surgically sterile. Women of childbearing potential (WOCBP) must have a negative urine pregnancy test (UPT) at Baseline.

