6.4.2 Visit 2 (Day 0): Baseline

The subject will return to the clinic and will be queried for any changes in health status since the previous visit, including concomitant medications and therapies. A urine pregnancy test with negative result confirmed will be performed for all WOCBP. The Hand Eczema Severity Index and Investigator's Global Assessment will be completed. Baseline reading of local skin reactions will be assessed prior to IP application. The Subject's Local Dermal Tolerability Assessment will be performed. IP will be dispensed to the subject. IP will then be dispensed and subject will apply the first dose in clinic. The subject diary will be dispensed. Digital photographs will be taken at proximal and distal views of both the dorsal as well as palmar surfaces of the subject's hand (treatment area). The subject will be scheduled to return to clinic for Visit 3 in accordance with the treatment window.

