6.4.4 Visit 4 (Day 28): Ending Follow-Up | ET | EOS

The subject will return to the clinic and will be queried for any changes in health status since the previous visit, including concomitant medications and therapies. A brief physical exam will be performed and vital signs will be taken. The Hand Eczema Severity Index and Investigator's Global Assessment will be completed. Local skin reactions will be assessed. The Subject's Local Dermal Tolerability Assessment will be performed. IP will be dispensed at the beginning of the study and collected at the end of the study. IP is to be applied at least once before the subject comes in for the scheduled visit. The subject diary will

be reviewed and collected. Digital photographs will be taken at proximal and distal views of both the dorsal as well as palmar surfaces of the subject's hand (treatment area).

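### For a completer, adverse event reporting closes on the day of the last application and no pregnancy test follows the first, so a pregnancy under exposure is captured only if the subject knows of it and reports it by Visit 4

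*Combined protocol and SAP*

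**What the plan says.** **When reporting ends.** Section 6.1.1.4: "Reporting of adverse events will terminate on the last day of study follow-up". The same section requires serious events, and non-serious events possibly related to treatment, to be followed until they resolve or are judged chronic or stable. That rule concerns events already identified.

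**When treatment ends.** The final visit is headed "6.4.4 Visit 4 (Day 28): Ending Follow-Up | ET | EOS". On that day "IP is to be applied at least once before the subject comes in for the scheduled visit", and the schedule in Section 6.3 also ticks product application at Visit 4. On supply, "IP will be dispensed at the beginning of the study and collected at the end of the study". No later visit or call is scheduled.

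**Pregnancy testing.** Inclusion criterion 7 (Section 4.1) says that women of childbearing potential "must have a negative urine pregnancy test (UPT) at Baseline". Section 6.4.2 repeats this for Visit 2: "A urine pregnancy test with negative result confirmed will be performed for all WOCBP". Later in the same paragraph, "IP will then be dispensed and subject will apply the first dose in clinic". The UPT row in Section 6.3 has one tick, at Visit 2, and the Visit 3 and Visit 4 procedures list no test.

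**Status of pregnancy.** Section 6.1.1.2: "Pregnancy should always be considered as a serious adverse event". A serious adverse event form is then required.

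**Mitigation.** Criterion 7 also requires effective contraception unless the woman is post-menopausal or surgically sterile. Exclusion criterion 1 removes women who plan a pregnancy during the study. Subjects are asked about their health and adverse events at Visits 3 and 4.

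**The concern.** The protocol defines an event as serious in every case, but schedules no test for it once exposure has begun and stops accepting new reports on the last day of exposure. Pregnancy becomes apparent only some time after it begins, so a window that ends with treatment is shortest for the conceptions nearest the end.

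Safety is the stated secondary objective, and Section 7.2.8.2 plans a table of serious events. If that table shows no pregnancies, the reader cannot tell how far this reflects contraception and small numbers, and how far it reflects observation stopping before a pregnancy could be recognised.

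**Working it through.** The plan gives no figure on this point to reproduce. The check is a timeline, then a sensitivity calculation on assumed inputs.

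**Step 1: off-treatment reporting window (completers).**
- Last application: the day of Visit 4 (Sections 6.3 and 6.4.4).
- Reporting closes: last day of follow-up, read as Visit 4 because nothing later is scheduled.
- Window = 28 − 28 = 0 days. It is also 0 at either end of the visit window (25 − 25, 31 − 31).

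**Step 2: tests after first exposure.** There is one UPT, at Visit 2 before the first dose. Tests between first and last application: 0 over 28 days (25 to 31 with the Visit 4 window). The scheduled tests therefore find 0% of on-treatment conceptions. Self-report is a separate route and is not counted here.

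**Step 3: what a UPT at Visit 4 would find.** Assumptions, not in the documents: a urine test turns positive L days after conception, with L = 14 (range 10 to 17), and conceptions are spread evenly over Days 0 to 28. The share detectable on Day 28 is (28 − L)/28.

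| L (days) | Calculation | Share found |
|---|---|---|
| 10 | 18/28 | 64% |
| 14 | 14/28 | 50% |
| 17 | 11/28 | 39% |

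A shorter assumed lag of 7 days would give 21/28 = 75%. The figure is driven by the assumption, but under any of these lags a Visit 4 test alone leaves a quarter or more unfound.

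Conceptions in the L days before Day 0 would be missed at baseline and exposed throughout. All of them would show by Day 28. If they are included at the same rate, the share found is 28/(28 + L): 28/38 = 74%, 28/42 = 67% and 28/45 = 62% for L = 10, 14 and 17.

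**Step 4: how long reporting must stay open.** A conception on the last treatment day could first test positive L days later: Day 28 + 10 = 38 to Day 28 + 17 = 45. A 30-day window closes on Day 58, leaving 30 − 17 = 13 days beyond the longest assumed lag.

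**Step 5: absolute scale (illustrative only).** The documents do not give the number of women of childbearing potential. Assume n = 5 to 20 and a per-woman pregnancy risk p = 0.1% to 1% over the study. The chance of at least one pregnancy is 1 − (1 − p)^n. This runs from 1 − 0.999^5 = 0.5% to 1 − 0.99^20 = 18%.

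**The case against.** **The subject can report it.** A reader might infer that a pregnancy under exposure can never come to light. The documents do not support that. Adverse events are ticked at Visits 3 and 4, health status is queried at both, and Section 6.1.1.2 accepts volunteered reports. A pregnancy reported by Day 28 must be recorded as serious and followed. What remains is narrower: questioning cannot elicit what the subject does not yet know, and it ends at Visit 4.

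**Contraception is required, and women planning pregnancy are excluded.** This stands. It lowers the probability, and a report of no pregnancies would partly reflect it. It does not detect a failure.

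**The percentages rest on assumption.** This also stands. Lag and even spread are both assumed, and the shares are conditional on a conception having occurred. The case for an open reporting period does not depend on the exact value, only on the lag being greater than zero.

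**Late skin reactions.** A reader might extend the point to reactions that first appear after the last application. Nothing in the documents indicates such a risk, and local skin reactions are assessed at Days 0, 14 and 28. The point is confined to pregnancy and serious events.

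**Limits of the text.** The zero-day gap applies to completers; in an early terminator the last application may precede the termination visit. The last day of study follow-up is not defined. If it meant the whole study's last day, earlier subjects would have some open time but no contact or instruction to use it, and the last subject would still have none. The consent pages are not available here, so any instruction in them to report a later pregnancy cannot be checked.

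**Conclusion.** The point holds in a limited form. For a completer, the last application and the close of reporting fall on the same day, and no scheduled pregnancy test follows first exposure. A pregnancy conceived on treatment, or too early to show on Day 0, is captured only if the subject already knows of it and reports it by Visit 4. One recognised later falls outside the reporting window, although the protocol would class it as serious.

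The expected number is small in a 28-day study of 20 subjects with required contraception, and no efficacy analysis is affected. This is an inexpensive improvement to safety ascertainment, not a flaw that undermines the trial. The timeline follows from the schedule, with the end of follow-up read as each subject's Visit 4. The 39% to 64% and the 0.5% to 18% rest wholly on the stated assumptions.

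**What to change.** 1. **Section 6.1.1.4 (essential).** Keep reporting of serious adverse events and pregnancies open for a stated period after the last application, for example 30 days. Subjects would self-report, with an exit instruction given at Visit 4. No extra visit is needed.
2. **Sections 6.3 and 6.4.4 (minor addition).** Repeat the existing UPT for women of childbearing potential at Visit 4 or early termination.
3. **Section 6.1.1.2 (consequential wording).** The 7-business-day limit for reporting serious events runs from the beginning of the event. For a pregnancy that limit may pass before anyone can know of it, so the text should say how it applies.

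**Cost.** At most 20 urine strips, a wording change and an exit instruction. Database lock waits up to the chosen period after the last subject's final visit, or late serious events are added after lock. Any pregnancy detected is followed under the existing rule, which may take months. Self-report after exit is passive, so capture will still be incomplete.

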6.1.1.5 Protocol Deviations Due to an Emergency or Adverse Event

Deviations from the protocol will be determined as allowable on a case-by-case basis. All protocol deviations and the reasons for such deviations must be noted on the CRF.

6.1.1.6 Study Medication and Treatment

The medication that a subject will be randomized to apply throughout the study will either be the active investigational product (AFX 5931) or the inactive vehicle product. After applying the IP for the first time at the clinic/study site under supervision of the health staff, subjects will, subsequently, be responsible for applying the treatment independently (twice daily) and recording each application on a subject diary.

6.1.1.7 Photography

Digital photographs will be taken at proximal and distal views of both the dorsal as well as palmar surfaces of the subject's hand (treatment area).

6.2 Laboratory Variables

Laboratory variables are not applicable to this study.

6.3 Schedule of Visits:

CCCR 08-2018	Visit 1	Visit 2	Visit 3	Visit 4
n=20	Day [-30] – [-1]	Day 0	Day 14	Day 28
Study Assessments		±1 Day	± 2 Days	± 3 Days
Informed Consent	X			
Demographics	X			
Inclusion/Exclusion Criteria	X			
Medical/Dermatological History	X			
Fitzpatrick Skin Phototype	X			
Brief Physical Examination	X			X
Vital Signs	X			X
UPT for WOCBP		X		
Hand Eczema Severity Index	X	X	X	X
Investigator's Global Assessment	X	X	X	X
Local Skin Reaction Assessment		X	X	X
Subject's Local Dermal Tolerability Assessment		X	X	X
Apply Investigational Product (IP)		X	X	X
IP Accountability (Dispensing/Collecting)		X	X	X
Subject Diary (Dispense/Review/Collect)		D	R	R/C
Digital Photographs	X	X	X	X
Concomitant Medications/Therapies	X	X	X	X
Adverse Events	X	X	X	X
Exit Case Report Form				X

6.4 Observations by Visit

6.4.1 Visit 1 (Day -30 to -1): Screening

Subjects can be screened up to 30 days prior to Visit 2/Baseline. If applicable, qualified subjects can washout from prohibited medications and/or therapies prior to Baseline (after obtaining consent). Subjects who require screening period or washout for longer than 30 days will be re-consented but may still be enrolled in the study if they otherwise meet enrollment criteria.

The study requirements and procedures will be reviewed and written informed consent must be obtained prior to the initiation of any study-related procedures. Demographics, inclusion/exclusion criteria, medical/dermatological history, and concomitant medications and therapies will be reviewed to determine eligibility. A brief physical exam will be performed, vital signs will be taken, and Fitzpatrick Skin Phototype will be determined. The Hand Eczema Severity Index and Investigator's Global Assessment will be completed. Digital photographs will be taken at proximal and distal views of both the dorsal as well as palmar surfaces of the subject's hand (treatment area). The subject will be scheduled for Visit 2 (Baseline).

6.4.2 Visit 2 (Day 0): Baseline

The subject will return to the clinic and will be queried for any changes in health status since the previous visit, including concomitant medications and therapies. A urine pregnancy test with negative result confirmed will be performed for all WOCBP. The Hand Eczema Severity Index and Investigator's Global Assessment will be completed. Baseline reading of local skin reactions will be assessed prior to IP application. The Subject's Local Dermal Tolerability Assessment will be performed. IP will be dispensed to the subject. IP will then be dispensed and subject will apply the first dose in clinic. The subject diary will be dispensed. Digital photographs will be taken at proximal and distal views of both the dorsal as well as palmar surfaces of the subject's hand (treatment area). The subject will be scheduled to return to clinic for Visit 3 in accordance with the treatment window.

6.4.3 Visit 3 (Day 14): Follow-Up

The subject will return to the clinic and will be queried for any changes in health status since the previous visit, including concomitant medications and therapies. The Hand Eczema Severity Index and Investigator's Global Assessment will be completed. Local skin reactions will be assessed. The Subject's Local Dermal Tolerability Assessment will be performed. IP will be dispensed at the beginning of the study and collected at the end of the study. IP will be applied by the subject at home in the evening, consistent with their usual twice daily dosing. The subject diary will be reviewed. Digital photographs will be taken at proximal and distal views of both the dorsal as well as palmar surfaces of the subject's hand (treatment area). The subject will be scheduled to return to clinic for Visit 4 in accordance with the treatment window.

6.4.4 Visit 4 (Day 28): Ending Follow-Up | ET | EOS

The subject will return to the clinic and will be queried for any changes in health status since the previous visit, including concomitant medications and therapies. A brief physical exam will be performed and vital signs will be taken. The Hand Eczema Severity Index and Investigator's Global Assessment will be completed. Local skin reactions will be assessed. The Subject's Local Dermal Tolerability Assessment will be performed. IP will be dispensed at the beginning of the study and collected at the end of the study. IP is to be applied at least once before the subject comes in for the scheduled visit. The subject diary will

be reviewed and collected. Digital photographs will be taken at proximal and distal views of both the dorsal as well as palmar surfaces of the subject's hand (treatment area).

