Study Design:	This is a double-blind, pilot study with 20 subjects to determine the tolerability and efficacy of topical AFX 5931 in the treatment of mild to moderate hand dermatitis. Subjects are screened up to 30 days before the baseline visit. Subjects who meet the eligibility criteria may qualify for the study. Subjects will be randomized in a 3:1 ratio to receive either the active or vehicle medication. 15 subjects will receive the active, therapeutic product and 5 subjects will receive the inactive, vehicle product. Subjects will complete 4 study visits according to the following 4-week timeline: Day [-30] – [-1] (Screening), Day 0 (Baseline), Day 14 (Follow-Up), Day 28 (Follow-up ET EOS). At Visit 2, IP will be dispensed and baseline readings of efficacy as well as safety/tolerability assessments will be obtained prior to application of the IP. Subjects will apply IP twice daily and compliance will be monitored by periodically reviewing the subject diary. The evaluations that will be used to measure efficacy of the product will be the Investigator's Global Assessment and Hand Eczema Severity Index. The Subject's Local Dermal Tolerability Assessment and Local Skin Reaction Assessment will be used throughout the course of the study to evaluate tolerability. Additionally, the actions that will be taken to evaluate safety will be the monitoring of adverse events, vital signs, and changes in concomitant medications. Digital photographs will be taken at each visit (excluding Visit 3).

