3.2 Overview

This is a double-blind, pilot study with 20 subjects to determine the tolerability and efficacy of topical AFX 5931 in the treatment of mild to moderate hand dermatitis. Subjects are screened up to 30 days before the baseline visit. Subjects who meet the eligibility criteria may qualify for the study. Subjects will be randomized in a 3:1 ratio to receive either the active or control medication, in which 15 subjects will receive the active, therapeutic product and 5 subjects will receive the inactive, vehicle product. Subjects will complete 4 study visits according to the following 4-week timeline: Day [-30] – [-1] (Screening), Day 0 (Baseline), Day 14 (Telephone Call), Day 28 (Follow-up | ET | EOS). At Visit 2, IP will be dispensed and baseline readings of efficacy and safety/tolerability assessments will be obtained prior to application of the IP. Subjects will apply IP twice daily and compliance will be monitored by reviewing the subject diary periodically throughout the study. The assessments that will be used to evaluate efficacy of the product will be the Hand Eczema Severity Index and Investigator's Global Assessment. The Subject's Local Dermal Tolerability Assessment and Local Skin Reaction Assessment will be used throughout the course of the study to evaluate tolerability. Additionally, the actions that will be taken to evaluate safety will be the monitoring of any adverse events or concomitant medications. Digital photographs will be taken at each visit (excluding Visit 3).

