7.2.8 Efficacy Analyses

Efficacy variables will be analyzed at the time points shown in the visit schedule.

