7.2.8.1 Primary Efficacy Analyses

This study is concerned with the efficacy of topical AFX 5931 in the treatment of mild to moderate hand dermatitis. Changes in clinical scores recorded via the Hand Eczema Severity Index and Investigator's Global Assessment will be the primary modes of efficacy evaluation.

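### Efficacy scores are read before any product at baseline but after a required application at Day 28, with no dose-to-scoring interval set, so within-arm change can include a short-lived surface effect (minor)

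*Combined protocol and SAP*

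**What the plan says.** **Baseline.** The Synopsis (Study Design) requires that "baseline readings of efficacy as well as safety/tolerability assessments will be obtained prior to application of the IP", and section 3.2 repeats the rule. Section 6.4.2 then has the first application made at the site: "IP will then be dispensed and subject will apply the first dose in clinic". The same section lists the baseline photographs after that dose.

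**Day 14.** Section 6.4.3 has HECSI and IGA completed in clinic and says of dosing only: "IP will be applied by the subject at home in the evening, consistent with their usual twice daily dosing". (Section 3.2 calls Day 14 a telephone call. That is a separate inconsistency; I follow 6.3 and 6.4.3, which make it a clinic visit.)

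**Day 28.** Section 6.4.4 has both scores completed in clinic and states: "IP is to be applied at least once before the subject comes in for the scheduled visit".

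**Schedule.** The IP application row in section 6.3 is marked at Visits 2, 3 and 4, without saying whether it comes before or after scoring.

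**Analysis.** Section 7.2.8.1 makes "Changes in clinical scores recorded via the Hand Eczema Severity Index" and the IGA the main efficacy measures. Section 7.2.8 adds: "Efficacy variables will be analyzed at the time points shown in the visit schedule". Section 7.2.1 plans confidence intervals for success proportions, and chi-square, relative risk, odds ratio, independent-samples t-test and ANOVA.

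Nowhere does the protocol set a minimum time from last application to scoring, ask for clean hands, or require the time of the last dose to be recorded at the assessment.

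**The concern.** Both scores grade surface signs: scaling, redness and cracking or fissures (section 9.0). A product on the skin could change how these look for a few hours without changing the disease. Scale might be less visible, or redness might rise with rubbing. The dosage form is not given, so neither the direction nor the size can be predicted.

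Baseline is free of any such effect by rule, while Day 28 is open to it by instruction. Change from baseline within each arm can then mix a transient effect with treatment response, and so can each arm's success proportion and its interval. With only 5 vehicle subjects, readers of a pilot are likely to look closely at change in the active arm alone. If the time of the last dose is not captured, the question cannot be examined afterwards.

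**Working it through.** **Order of dosing and scoring**

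| Visit | Scoring relative to IP | Source |
|---|---|---|
| Day 0 | Before the first dose, by rule | Synopsis, 3.2, 6.4.2 |
| Day 14 | Evening dose placed at home; an earlier dose that day is implied, its order not given | 6.4.3 |
| Day 28 | After at least one application; interval not given | 6.4.4 |

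The Day 28 sentence does not name the day of that application. After four weeks of twice-daily use, however, it has meaning only as a dose on the day of the visit.

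**HECSI.** Section 9.0 grades six signs 0 to 3 (sum at most 18), multiplies the sum by an extent of 0 to 4, and adds over five areas. The plan's maximum is reproduced: 5 × 18 × 4 = 360. With extent e unchanged, one grade in one sign in one area moves the total by e, which is 1 to 4 points. The same change in all five areas moves it by 5e, which is 5, 10, 15 or 20 points; this is an extreme case.

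**IGA.** Entry requires a score of 2 or 3. One grade is 1/2 or 1/3 of the largest possible improvement.

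**Success proportions.** One reclassified subject moves the active proportion by 1/15 = 6.7 percentage points and the vehicle proportion by 1/5 = 20. This holds for any misread score, so it gives scale and not an estimate of the effect. Success is not defined in 7.2.1, so the influence on the proportions, relative risk and odds ratio cannot be sized.

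**Between-arm mean.** Assume true mean changes of −20 (active) and −15 (vehicle) and a shared shift d. The difference is (−20 + d) − (−15 + d) = −5 for d = −10, −4, 0, 4 and 10.

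**Noise.** The plan gives no SD, so I assume 10 to 20 points for HECSI change, with a shift d present in half the subjects.

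- Added SE = d × √(0.25 × (1/15 + 1/5)) = 0.258d.
- Base SE = SD × √(1/15 + 1/5) = 0.516 SD.
- Ratio of total to base SE = √(1 + d²/(4 SD²)).

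| d (points) | SD 10 | SD 15 | SD 20 |
|---|---|---|---|
| 1 | +0.12% | +0.06% | +0.03% |
| 4 | +2.0% | +0.9% | +0.5% |
| 10 | +11.8% | +5.4% | +3.1% |

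**If the effect differed between arms.** The bias would equal the difference. An assumed 0.4 SD on active and 0.2 SD on vehicle gives 0.2 SD. With 15 versus 5 subjects and two-sided 0.05, the difference detectable with 80% power is (1.960 + 0.842) × 0.516 = 1.45 SD by normal approximation (power is 76% by noncentral t).

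**The case against.** The strongest reply is that vehicle subjects follow the same instruction. The test that 7.2.1 names for means, the independent-samples t-test, compares arms, no paired or within-arm test is named, and the ANOVA factors are unspecified. An equal effect cancels in the mean difference, and nothing in the documents suggests an unequal one. This stands, and it is why the point is minor. It does not protect the descriptive change within an arm or each arm's success proportion.

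A reader might infer that the Day 14 to Day 28 course is distorted. The documents do not support that as a finding. Section 7.2.8 names time points but no contrast between visits. The reference to usual twice-daily dosing in 6.4.3 may mean that both visits follow an ordinary morning dose. A difference between the two visits is possible but is not stated.

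A reader might also infer that subjects are scored just after dosing. Section 6.4.4 gives no interval, so the dose could be hours old. What is established is that the interval is uncontrolled.

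The noise model can be criticised too: 6.4.4 requires the dose of everyone, so at Day 28 only the interval varies. That is fair, and the half-and-half split is illustrative.

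Finally, applications are entered in the diary (5.4, 6.1.1.6), and section 8.7 refers to SOPs and other written instructions. These are not shown and may cover part of the gap.

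**Conclusion.** The point holds as a minor one. A stated rule, and not only a missing detail, makes the Day 28 reading post-dose while baseline is dose-free, and the Day 14 order is left open. At risk are within-arm change in HECSI and IGA and the per-arm success proportions.

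The size is unknown. Shifts of 1 to 4 HECSI points are what one grade in one sign in one area would produce, and under the stated assumptions they widen the standard error of the between-arm difference by 0.03% to 2.0%. The 10-point row is purely assumed.

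Two stronger conclusions are not supported. The active versus vehicle mean difference is not shown to be biased; that would need an effect that differs by arm. Nor is a pre-dose baseline, or scoring during ongoing treatment, a fault: baseline must precede treatment. The weakness is the uncontrolled timing of the last dose at later visits. The conclusion assumes that recently applied product can alter the visible signs at all, which the documents neither show nor exclude.

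**What to change.** In 6.4.4 replace the sentence requiring a pre-visit application, and align 6.4.3, with text such as:

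> At Visits 3 and 4, HECSI and IGA are scored on clean, dry hands free of visible product, at the same minimum interval since the last IP application (for example, the morning dose is held until after scoring). The date and time of the last application are recorded. A dose held under this rule is not a missed dose under 5.4. At an early-termination visit only the time of last application is recorded.

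Footnote the IP application row in 6.3 to show application after scoring, and in 6.4.2 take the baseline photographs before the first dose. At Visit 4 the held dose can be applied in clinic after scoring. Local skin reaction and itch can be read after it if the sponsor wants post-dose tolerability.

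**Cost.** Protocol wording, one table footnote, one CRF or diary field and a line in the subject instructions. Sample size and alpha do not change. One dose is delayed at each of two visits, out of about 57 (two a day on Days 0 to 27 is 56, plus one on Day 28). If the Visit 4 dose is not given in clinic, 1/57 = 1.8% of applications is lost. If tolerability, the secondary objective, is read before dosing, brief post-dose irritation is slightly less likely to be seen; reading it after the clinic dose at Visit 4 limits that loss.
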